6.4.2. Permanent Discontinuation of Study Medication

During the course of this long-term study, it is anticipated that patients may permanently discontinue study medication (sparsentan or irbesartan) for any of the following reasons:

- Receipt of kidney transplant or initiation of RRT
- Any SAE, AE of interest (AEOI; see [Section 10.3](#)), clinically significant laboratory abnormality, intercurrent illness, or other medical condition that indicates to the Investigator that continuation on study medication is not in the best interest of the patient
- Significant protocol deviation (ie, patient failed to meet entry criteria or did not comply with protocol requirements resulting in an unacceptable risk to the patient's health)
- Investigator discretion
- Patient (or parent/legal guardian) decision to stop study medication
- Patient pregnancy
- Diagnosis of Class II-IV CHF
- Hyperkalemia resistant to treatment (see Appendix B, [Section 15.2.2](#) for hyperkalemia management guidelines)
- Termination of the study by the Sponsor, US Food and Drug Administration (FDA), or other regulatory authorities (see [Section 13.4.5](#))
- Lost to follow-up

Therapy to treat relapse (that is a new or substantial change in immunosuppression) during the study is not a reason for permanent study medication discontinuation.

Patients who permanently discontinue study medication during the double-blind period should be encouraged to continue study visits through Week 112 for continued collection of safety and efficacy data despite stopping study medication, but may withdraw consent at any time (see [Section 6.5](#)). Patients who agree to continue regularly scheduled study visits will complete the End of Treatment (EOT) assessments listed in the schedule of events ([Section 15.1](#)) as close as possible to the patient's last dose of study medication. The visit data, including the primary reason for discontinuation of study medication, will be recorded on the EOT electronic case report form (eCRF). Subsequent study visit data will be recorded on the visit-specific eCRF, and the patient's final study visit will be recorded on the End of Study (EOS) eCRF.

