3.2.4. Safety Endpoints

Safety endpoints include:

- Changes from baseline of the double-blind period in body weight, vital signs, physical examination, peripheral edema, 12-lead electrocardiogram, and clinical laboratory parameters
- Changes from baseline of the double-blind period in lipid profile (total cholesterol and triglycerides, low-density lipoprotein cholesterol [LDL-C], very low-density lipoprotein cholesterol [VLDL-C], and high-density lipoprotein cholesterol [HDL-C])
- Changes from baseline of the double-blind period in serum albumin and serum potassium at each visit
- Incidence of treatment-emergent adverse events (TEAEs) during the double-blind period

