6.5.4. Visit Windows

A visit window method will be applied to determine analysis visits across the study for efficacy and safety endpoints based on laboratory results, including eGFR and quantitative urinalysis (including UP/C and FPFE). If a patient has multiple assessments (including unscheduled visits) within a visit window, the value closest to the target day for that visit will be selected for analysis. If more than 1 assessment is equidistant to the target day, then the latest value will be selected. For efficacy analysis visits on or prior to Week 108, only assessments while the patient is on randomized treatment should be included (see [Section 8.1](#) for definition of on treatment).

For quantitative urinalysis endpoints that are derived as the geometric mean of replicates collected over several days, all replicates used to derive the average should be mapped to the same analysis visit per Table 2, should be within 5 days of each other, and should all have been collected while the subject was on study medication. For the derivation of baseline, all replicates must have been collected on or prior to the date of reference dose. The study day of the endpoint will be derived as the maximum study day of the replicates used in the derivation.

If a patient is missing a UP/C assessment at a given analysis visit due to only having 1 urine sample available within 5 days, the available single assessment closest to the target day for that visit will be selected for sensitivity analysis.

The following visit windows for the double-blind period are defined for endpoints based on laboratory results. Visit windows for the OLE will be defined in a separate SAP.

Table 2: Visit Windows (Study Days)

Analysis Visit	Relative Target Day	Analysis Visit Window (Study Days)	
		eGFR and Safety Labs	Quantitative Urinalysis
Week 2	15	2 – 22	N/A
Week 4	29	23 – 36	N/A
Week 6	43	37 – 50	2 – 71
Week 8	57	51 – 71	N/A
Week 12	85	72 – 127	72 – 127
Week 24	169	128 – 211	128 – 211
Week 36	253	212 – 295	212 – 295
Week 48	337	296 – 379	296 – 379
Week 60	421	380 – 463	380 – 463
Week 72	505	464 – 547	464 – 547
Week 84	589	548 – 631	548 – 631
Week 96	673	632 – 715	632 – 715
Week 108 ¹	757	716 – 771	716 – 771
Week 112 ¹	785	>771	>771
4-week after EOT ²	785 ¹ or Last Dose Date + 28 ³	>771 ¹ or 2-12 weeks (14-84 days) after Date of Last Dose ³	>771 ¹ or 2-12 weeks (14-84 days) of Date of Last Dose ³

¹ For patients who completed the planned randomized treatment period.

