² Efficacy endpoints only.

³ For patients who discontinued the randomized treatment early.

eGFR = estimated glomerular filtration rate; EOT = End of Treatment; N/A = not applicable.

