10. SAFETY AND TOLERABILITY

Safety analyses will be conducted using the Safety Analysis Set at both interim and final analysis. At the interim analysis, all available data will be summarized. Unless otherwise noted, all safety analyses will be conducted using on-study data. All safety analyses specified below refer to the double-blind period only, except where noted. If >5% of patients initiate RRT while on study, select summaries excluding results after initiation of RRT may be prepared.

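### SAP Table 2 closes the Week 108 and Week 112 windows to patients who stopped treatment early, so by-visit safety laboratory summaries change population after Week 96

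*SAP*

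**What the plan says.** SAP section 6.5.4 governs both kinds of endpoint: "A visit window method will be applied to determine analysis visits across the study for efficacy and safety endpoints based on laboratory results". Table 2 then has one window column for eGFR and safety labs together and one for quantitative urinalysis.

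- The rows from Week 2 to Week 96 carry no footnote. Week 96 ends on Day 715.
- The Week 108 row (Day 716-771) and the Week 112 row (after Day 771) carry footnote 1: "For patients who completed the planned randomized treatment period".
- The 4-week-after-EOT row is the only one that serves the complementary group, defined in footnote 3: "For patients who discontinued the randomized treatment early". Footnote 2 restricts that row: "Efficacy endpoints only".
- A separate rule in the same section handles off-drug efficacy data: "For efficacy analysis visits on or prior to Week 108, only assessments while the patient is on randomized treatment should be included". SAP section 8.1 counts a value as on treatment up to 3 days after the last dose.

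For safety, SAP section 10 states: "Unless otherwise noted, all safety analyses will be conducted using on-study data". Section 10.4 summarizes laboratory results at each scheduled post-baseline visit, and section 3.2.4 names as an endpoint: "Changes from baseline of the double-blind period in serum albumin and serum potassium at each visit". Protocol section 6.4.2 says that patients who permanently stop study medication in the double-blind period "should be encouraged to continue study visits through Week 112 for continued collection of safety and efficacy data".

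**The concern.** Safety labs of patients who have stopped drug are meant to count, and through Week 96 they do. After Day 715 Table 2 offers these patients no window. The same off-drug patient is in the Week 96 summary and absent from Week 108, although still attending. Nothing in SAP section 10 announces that change of population.

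The reasons for stopping listed in protocol section 6.4.2 include treatment-resistant hyperkalemia, clinically significant laboratory abnormalities and the start of renal replacement therapy. The patients left out are therefore plausibly different on the very tests being summarized. A reader who compares potassium, albumin, or by-visit CTCAE shifts at Week 96 with those at Week 108 could take a change of population for a change over time.

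There is a smaller consequence for efficacy. SAP sections 8.5.1.1 and 8.5.1.2 take on-treatment eGFR for each patient, but time in those models is the analysis visit, and section 6.6.1.1 sends all data through the Table 2 windows. A value without an analysis visit cannot enter the model, even if it was taken on treatment.

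**Working it through.** **Window limits.** Target day = 7 × week + 1, which gives 673, 757 and 785 for Weeks 96, 108 and 112. The limits are midpoints of adjacent targets: (673 + 757)/2 = 715 and (757 + 785)/2 = 771. Both match Table 2. The limits are sound; the only question is who may use the rows.

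**What footnote 1 means.** Footnote 3 describes its complement as stopping randomized treatment early. Footnote 1 therefore refers to completing treatment, not follow-up.

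**An off-drug patient who keeps attending.** Suppose drug stops at Week 40 and every visit is kept.
- Weeks 48 to 96: safety labs map, because the on-treatment rule covers efficacy only.
- Day 757: past Day 715, and Week 108 is closed by footnote 1.
- Day 785: Week 112 is closed by footnote 1.
- 4-week-after-EOT row: closed to safety labs by footnote 2.

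**Size for safety labs.** The documents give no discontinuation or retention rate, so these are assumptions.
- With 20-30% stopping and 50-70% of those attending: 0.20 × 0.50 = 10% to 0.30 × 0.70 = 21% of randomized patients have labs without a visit.
- With 75% completers and 15% off-drug attenders, the omitted share of available values is 0.15/(0.75 + 0.15) = 16.7%. The visit mean then moves by 0.167 times the completer-minus-discontinuer difference, for which the documents give no value.

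**A late discontinuer's eGFR.** Take a last dose on Day 735 and an eGFR on Day 736. The value is on treatment (1 day after last dose). It is past Week 96, barred from Week 108, and too early for the window of 14-84 days after last dose. It has no visit.
- Earliest last dose at risk: 716 − 3 = Day 713.
- Latest: Day 749, the day before the Week 108 visit opens at 757 − 7 = Day 750. A patient who takes the last dose at a Week 108 visit on or after Day 750 has finished on schedule.
- Width: 749 − 713 + 1 = 37 days. With 25% discontinuation spread evenly over 757 days, 0.25 × 37/757 = 1.2%, or 3.7 of 300. For 10, 20, 30 and 40% discontinuation the counts are 1.5, 2.9, 4.4 and 5.9.

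**Weight in the slope analysis.**
- Such a patient keeps up to 12 of 13 post-baseline visits. Without Week 108 the spread of visit times (sum of squares, in years squared) falls from 6.26 to 4.58, so the residual-error part of that patient's slope variance rises by 6.26/4.58 − 1 = 37%. For Weeks 6-108 the rise is 38%.
- With an assumed between-patient slope SD of 4-8 and residual SD of 5-8, the patient's weight falls by about 2-12%.
- The plan's total-slope power (150 per arm, difference 2.1, SD 5.50) reproduces as 0.911, in line with the stated minimum of 90%. If 6 patients each lose 15% of their information, deliberately above that range, the loss is 6/300 × 0.15 = 0.3% and power is 0.910. The change is under 0.1 percentage point.

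**The case against.** **The primary slope is not threatened.** A reader might infer from the unmapped eGFR values that the primary result is at risk. The documents and the arithmetic do not support that. The count of about 4 is an upper bound. No visit is scheduled between Week 96 and Week 108, so a value is lost only if an end-of-treatment or unscheduled central-laboratory sample falls after Day 715 and within 3 days of last dose. Protocol section 6.4.2 asks only that end-of-treatment assessments be as close as possible to the last dose; a sample on the fourth day or later is excluded by the on-treatment rule anyway. This objection stands in full. What remains is a conflict with section 8.5.1.

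**Off-drug labs do not vanish from the safety analysis.** That too might be inferred, and it is wrong. Worst-value and last-value shift tables (SAP 10.4.1 and 10.4.2), the any-time liver listing (10.4.3) and by-patient listings (6.1) keep them, and no hypothesis test of laboratory safety is planned. The loss is confined to by-visit descriptive summaries.

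**The footnote may be a permitted exception.** SAP section 10 allows for exceptions that are noted elsewhere, and footnote 1 could be called one. That is arguable but weak. Footnote 1 does not mention safety data, and where the authors wanted a row confined to one type of endpoint, as in footnote 2, they said so. Section 10.4 gives no sign that the population changes after Week 96.

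**A completers-only Week 112 row can be defended.** Everyone is off study drug by then. Pooling completers 4 weeks off drug with patients off drug for a year or more mixes two conditions, and footnote 1 matches the completers-only ANCOVA in sections 8.7.2 and 8.7.3. For efficacy this is right, and no error arises there. For safety labs, Week 112 is less clear-cut than Week 108.

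**Conclusion.** The gap is real on the text. A non-completer's safety labs after Day 715 have no analysis visit, so the by-visit laboratory summaries, including the potassium and albumin endpoint and by-visit CTCAE shifts, move from on-study patients to treatment completers at the last two visits. Week 108 is the firm part. Under the assumed stopping and attendance rates this concerns 10-21% of randomized patients. Without a completer-versus-discontinuer difference, no effect on any safety conclusion can be shown.

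The eGFR effect is a specification conflict of negligible numerical weight: one value for each of at most about 4 of 300 patients under 25% uniform discontinuation. The values lost come just before stopping and may be informative, but they are too few to matter for power. No sample size, alpha level, hypothesis test or key safety display is called into question. The point is worth settling because programmers must otherwise choose between Table 2 and sections 8.5.1 and 10.

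**What to change.** - **Week 108 row:** remove footnote 1. The on-treatment rule in section 6.5.4 already excludes off-drug efficacy values, so the footnote does no work there. The quantitative urinalysis column has the same restriction and is corrected by the same edit.
- **Week 112 row:** limit footnote 1 to efficacy endpoints, which keeps it in line with sections 8.7.2 and 8.7.3.
- **Add one sentence** stating that safety labs on Day 716-771 and after Day 771 map for every patient in double-blind follow-up, whether on or off drug.
- **Optional:** because Week 112 is off drug for everyone, also show the Week 112 safety summary by treatment-completion status.

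The cost is SAP wording and the matching programming specification. Protocol section 6.4.2 already provides for collecting these data, so no new visits or samples are needed.

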6.5.5. Kidney Disease Quality of Life (KDQOL) Survey

KDQOL-36 is a short form questionnaire that includes the Short Form Health Survey (SF-12) as generic core plus the burden of kidney disease, symptoms/problems with kidney disease, and effects of kidney disease scales from the KDQOL-SF v1.3. Below are the included items:

- Items 1-12: SF-12 v2
- Items 13-16: Burden of kidney disease (4 items)
- Items 17-28b: Symptoms/problems of kidney disease (12 items)
- Items 29-36: Effects of kidney disease (8 items)

Each question in KDQOL-36 is pre-coded with a numeric value, and out-of-range responses will be recorded as missing. Missing values will not be imputed. Survey responses will be scored based on adaptations from the KDQOL-SF v1.3 scoring manual (Hays 1997) and SF-12 scoring guide (Maruish 2012), as outlined below:

1. For items 13 to 36, raw pre-coded numeric values will be transformed to 0 to 100 possible range, with the higher transformed scores always reflecting better quality of life. Scores present the percentage of total possible scores achieved. Transformations per items are specified in Table 3 below.

Table 3: Transformations of Pre-coded Values for KDQOL-36

Applicable Items	Pre-coded Value	Transformed Score (0-100)
Items 13-16	1	0
	2	25
	3	50
	4	75
	5	100
Items 17-27, 28a, 28b, 29-36	1	100
	2	75
	3	50
	4	25
	5	0

KDQOL = Kidney Disease Quality of Life.

2. The following 3 subscales will be computed as the average of available items (transformed scores) within each subscale:

Table 4: KDAQOL Subscales

Sub-scale	Average of Available Items (Transformed Scores)
Symptoms/Problems List	Items 17-28 (12 items)
Effects of Kidney Disease	Items 29-36 (8 items)
Burden of Kidney Disease	Items 13-16 (4 items)

KDAQOL = Kidney Disease Quality of Life.

3. For items 1 to 12, scale scores and physical (PCS) and mental component summary (MCS) measures will be computed using a norm-based method in the following steps:
 - Recode 4 items that require recoding; a higher score indicates better functioning:

Table 5: SF-12 v2 Items Recoding

Items	Response Choices	Pre-coded Item Value	Final Item Value
1 – General health	Excellent	1	5.0
	Very good	2	4.4
	Good	3	3.4
	Fair	4	2.0
	Poor	5	1.0
5 – How much did pain interfere with your normal work	Not at all	1	5
	A little bit	2	4
	Moderately	3	3
	Quite a bit	4	2
	Extremely	5	1
6a – Felt calm and peaceful 6b – Energy	All of the time	1	5
	Most of the time	2	4
	Some of the time	3	3
	A little of the time	4	2
	None of the time	5	1

SF-12 = Short Form Health Survey.

- After item recoding, a raw score is computed for each scale. This score is the simple algebraic sum of responses for all items in that scale, as shown below:

Table 6: SF-12 v2 Scale Items and Range of Possible Scores

Scale	Sum of Final Item Values	Lowest and Highest Possible Raw Scores	Possible Raw Score Range
Physical Functioning (PF)	Items 2a + 2b	2, 6	4
Role Physical (RP)	Items 3a + 3b	2, 10	8
Bodily Pain (BP)	Item 5	1, 5	4
General Health (GH)	Item 1	1, 5	4
Vitality (VT)	Item 6b	1, 5	4
Social Functioning (SF)	Item 7	1, 5	4
Role Emotional (RE)	Items 4a + 4b	2, 10	8
Mental Health (MH)	Items 6a + 6c	2, 10	8

SF-12 = Short Form Health Survey.

- Transform each raw scale score to a 0 to 100 scale using the formula shown below:

$$\text{Transformed scale} = \frac{(\text{Actual raw score} - \text{lowest possible raw score})}{\text{Possible raw score range}} * 100$$

- Next, standardize each scale using a z-score transformation by subtracting the mean 0 to 100 score observed in the 1998 general US population for each scale and dividing the difference by the corresponding scale standard deviation, as shown below:

Table 7: SF-12 v2 Z-Score Transformation Based on 1998 General US Population Means and Standard Deviations

Scale	Mean	Standard Deviation
Physical Functioning (PF)	81.18122	29.10558
Role Physical (RP)	80.52856	27.13526
Bodily Pain (BP)	81.74015	24.53019
General Health (GH)	72.19795	23.19041
Vitality (VT)	55.59090	24.84380
Social Functioning (SF)	83.73973	24.75775
Role Emotional (RE)	86.41051	22.35543
Mental Health (MH)	70.18217	20.50597

SF-12 = Short Form Health Survey; US = United States.

- Next, transform each scale z-score to the norm-based (50, 10) scoring. This is done by multiplying each z-score by 10 and adding the resulting product to 50. The norm-based scale scores will be used for analysis.
- To compute the PCS and MCS scores, multiply each scale z-score by its respective physical and mental factor score coefficient and summing the 8 products, as shown below:

Table 8: SF-12 v2 Factor Score Coefficients for PCS and MCS Derivation

Scale	Factor Score Coefficients	
	PCS	MCS
Physical Functioning (PF)	0.42402	-0.22999
Role Physical (RP)	0.35119	-0.12329
Bodily Pain (BP)	0.31754	-0.09731
General Health (GH)	0.24954	-0.01571
Vitality (VT)	0.02877	0.23534
Social Functioning (SF)	-0.00753	0.26876
Role Emotional (RE)	-0.19206	0.43407
Mental Health (MH)	-0.22069	0.48581

MCS = Mental Component Summary; PCS = Physical Component Summary; SF-12 = Short Form Health Survey.

- The final step for computation of PCS and MCS involves transforming the aggregate physical and mental summary scores to the norm-based (50, 10) scoring. This is done by multiplying each aggregate summary score from the previous step by 10 and adding the resulting product to 50. The norm-based scores will be used for analysis.

6.5.6. Pediatric Quality of Life Inventory (PedsQL)

The PedsQL (v4.0) instrument consists of developmentally appropriate modules: Child Self-Report (ages 8 to 12) and Teen Self-Report (ages 13 to 18). Each module is composed of 23 items comprising 4 dimensions:

- Physical Functioning: 8 items
- Emotional Functioning: 5 items
- Social Functioning: 5 items
- School Functioning: 5 items

The instrument will be scored in the following steps:

1. Transform each 0-4 scale items to 0 to 100 as follows: 0 = 100, 1 = 75, 2 = 50, 3 = 25, 4 = 0.
2. Create scale score for each dimension, as the sum of the items over the number of items answered. If more than 50% of the items are missing, the scale score for that dimension should not be computed. If <50% of the items are missing, impute the missing score using the mean of the completed items.
3. Create Psychosocial Health Summary Score as the sum of the items over the number of items answered in the Emotional, Social, and School Functioning Scales.
4. Create Physical Health Summary Score, which is equivalent to the Physical Functioning Scale Score.

5. Create Total Score as the sum of all the items over the number of items answered on all the Scales.

The 4-dimension scores, 2 summary scores, and Total Score will be used for analysis.

6.5.7. EQ-5D-5L

EuroQol, 5-dimension QOL instrument, version 5L (EQ-5D-5L) is a 2-part instrument consisting of the following:

- Descriptive system is comprised of the following 5 dimensions:
 - Mobility
 - Self-care
 - Usual activities
 - Pain/discomfort
 - Anxiety/depression
- EQ Visual Analogue Scale (EQ VAS)

For each dimension, respondents select 1 of 5 statements that best describes their health on that day. Each statement/level is pre-coded with a 1-digit number (1 to 5). Missing responses will be coded as “9.” The responses to the 5 dimensions are then concatenated to represent a patient’s health state. For example, “12345” represents a Mobility response of 1, Self-care response of 2, Usual activities response of 3, Pain/discomfort response of 4, and Anxiety/depression response of 5. The health states can be converted into a single index value based on country-specific value sets by using the crosswalk link function ([vanHout 2012](#)).

The EQ VAS records the respondent’s self-rated health on a vertical, visual analogue scale. The scale is numbered from 0 to 100, with 0 labeled as “the worst health you can imagine” and 100 labeled as “the best health you can imagine.”

6.5.8. EQ-5D-Y

EuroQol, 5-dimension QOL instrument, version Youth (EQ-5D-Y) is a child-friendly version of EQ-5D and consists of 2 parts: the same 5 dimensions as the EQ-5D-5L assessed with 3 levels, and the EQ VAS numbered from 0 to 100.

For each dimension, respondents select 1 of 3 statement best describes their health on that day. Missing responses will be coded as “9.” The responses to the 3 dimensions are then concatenated to represent a patient’s health state, similar to that in EQ-5D-5L. There is no value set available for EQ-5D-Y for conversion for a single index value.

6.5.9. eGFR Derivation

The eGFR for each baseline and post-baseline visit will be determined at the central laboratory using the CKD-EPI (Chronic Kidney Disease Epidemiology Collaboration; [Levey 2009](#)) formula for patients ≥ 16 years of age at the time of screening, and the Modified Schwartz formula for patients < 16 years of age at the time of screening ([Schwartz 2009a](#); [Schwartz 2009b](#)).

Missing central laboratory eGFR from subject visits for which serum creatinine is available will be derived using the appropriate age-based formula. For the derivation of eGFR per the Modified Schwartz formula, if height is missing for the subject visit then the last reported height within the central laboratory results will be used in the derivation.

